6.4 Criteria for Dose Reduction

Subjects taking the curcumin-containing mouth rinse that experience intolerable or prolonged (>14 days) grade 2 toxicity will receive the next lowest dose from the dose escalation part of the study.

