5.6 Determination of MTD

The MTD will be determined as follows: If a DLT occurs in any one of the 3 patients at a specific dose level, an additional 3 patients must be treated at that dose level to achieve statistical validity of the MTD. If 2 of the 6 patients (17%) at a dose level develop a DLT, the previous dose level will be used as the MTD. If no DLT is observed, then the MTD will be the highest dose. To ensure safety of subjects at each dose level, all assessments will be completed at Visit 5 for subjects at a dose level before another subject is given study drug at the

subsequent dose level.

6. Expected Adverse Events

Toxicities will be graded by health care providers using the Common Terminology Criteria for Adverse Events (CTCAE) Version 4.0 weekly after initiation of study mouth rinse until mucositis is resolved (Grade 0) (see Provider Assessment in calendar, section 5.2). Toxicities will be assessed by subject self-evaluation during study mouth rinse administration between clinic visits (see Subject Assessment in calendar, section 5.2).

Very few studies have reported any severe or serious side effects from curcumin and most studies have involved oral administration of curcumin. No major toxicity has been found in studies where curcumin is used short-term. Increased bleeding may occur due to inhibition of platelet aggregation (very rare). Possible other side effects associated with curcumin include: vomiting, nausea, rash and GI distress. In a study of subjects with colon cancer, oral curcumin at doses ranging from 0.45 to 3.6 gram/day for 1 to 4 months was associated with nausea and diarrhea and caused an increase in serum alkaline phosphatase and lactate dehydrogenase[15]. In one study of patients with advanced pancreatic cancer, 5 of the 17 patients receiving oral curcumin (8 gram/day) in combination with gemcitabine reported intractable abdominal pain after a few days to 2 weeks of curcumin intake[16]. In a recent study of topical curcumin for mucositis in juveniles and children[14], there were no oral adverse events documented and no systemic adverse events that possibly could be related to the use of the curcumin mouthwash.

Patients will receive full supportive care as appropriate. The rationale for treatment, dosage and the date of treatment will be recorded in the medical record.

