6.1 Dose-limiting Toxicity

DLT resulting from any treatment component of the study will be defined in the list below. There will be no dose reductions in response to DLT.

- Any grade 2 or greater allergic response
- Any grade 3 or greater toxicity

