6.2 Criteria for Subject Removal

A subject will be removed from the study for the following reasons:

- Dose limiting toxicity.
- No improvement in mucositis after 14 days of taking the study mouth rinse.
- Patient decision to withdraw consent or discontinue the study.
- Deemed by the physician to be the best medical interest of the patient.
- At the discretion of the investigator, patients who are non-compliant.

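### A grade 2 allergic response gets two incompatible instructions (6.1/6.2 against 6.4), and dose reductions under 6.4 do not enter the MTD rule in 5.6

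*Combined protocol and SAP*

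**What the plan says.** Section 6.1 defines two kinds of DLT: "Any grade 2 or greater allergic response" and "Any grade 3 or greater toxicity". It adds: "There will be no dose reductions in response to DLT".

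Section 6.2 opens with "A subject will be removed from the study for the following reasons", and a DLT is the first reason listed.

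Section 6.4 states: "Subjects taking the curcumin-containing mouth rinse that experience intolerable or prolonged (>14 days) grade 2 toxicity will receive the next lowest dose". The lower dose is to come from the levels of the escalation part. The sentence covers everyone taking curcumin, without limiting it to Part 1 or Part 2 and without excluding allergic events. What counts as intolerable is not defined.

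Section 5.6 gives the MTD rule in DLTs only: "If a DLT occurs in any one of the 3 patients at a specific dose level, an additional 3 patients must be treated"; "If 2 of the 6 patients (17%) at a dose level develop a DLT, the previous dose level will be used as the MTD"; and "If no DLT is observed, then the MTD will be the highest dose". Section 3 points to section 2 for a definition of the MTD, but section 2 lists only objectives, so 5.6 is the only rule.

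The dose table in section 3 starts at 0.33 g per dose (1 g/day). Part 2 assigns the MTD to a randomised curcumin arm of 23 subjects.

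**The concern.** The MTD is the primary objective, and it fixes the dose of the Part 2 curcumin arm. Two things are at stake.

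First, staff facing an intolerable or prolonged grade 2 allergic response cannot follow 6.1 and 6.2 and also follow 6.4. Staff facing a 6.4 event at the first dose level have no lower dose to give.

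Second, the protocol has a category of toxicity serious enough to take a subject off the assigned dose, yet the rule that names the maximum tolerated dose does not register it. The protocol also does not say whether a reduced subject still counts as a DLT-free subject at the assigned level, is replaced, or contributes to the lower level. Two sites or two readers could count the same subject differently.

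**Working it through.** **The rules side by side**

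| Event in a subject on curcumin | 6.1 / 6.2 | 6.4 | Counted in 5.6? |
|---|---|---|---|
| Grade 3 or higher, any type | DLT; no reduction; removed | Does not apply | Yes |
| Grade 2 allergic, intolerable or over 14 days | DLT; no reduction; removed | Next lowest dose | Yes |
| Grade 2 non-allergic, intolerable or over 14 days | Not a DLT | Next lowest dose | No |
| The same, at dose level 1 | Not a DLT | No lower dose in the table | No |

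The second row is a direct contradiction. In the third row all the sections can be followed together, so the fault there is a gap in the MTD rule. The fourth row is an instruction that cannot be carried out.

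**Limiting case for the third row.** Suppose all three subjects at the top level have intolerable non-allergic grade 2 toxicity and step down. The DLT count is 0 of 3. If no lower level produced a DLT either, 5.6 names the top level the MTD.

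**The plan's own figure.** The only percentage in the MTD rule is the 17% printed for 2 of 6. It does not reproduce: 2/6 = 33.3%, while 1/6 = 16.7%. That is a separate error and does not affect this point.

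**How often reductions might occur.** The documents give no reduction rate. Let q be the per-subject risk of a 6.4 reduction, assumed equal and independent across subjects, and taken over 0.1 to 0.5.

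- P(at least 1 of 3 steps down) = 1 − (1 − q)³. For q = 0.1: 1 − 0.729 = 0.271. For q = 0.5: 1 − 0.125 = 0.875.
- Expected reductions in the Part 2 curcumin arm = 23q. For q = 0.1: 2.3. For q = 0.5: 11.5.

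| q (assumed) | At least 1 of 3 reduced | Expected reduced of 23 |
|---|---|---|
| 0.1 | 27% | 2.3 |
| 0.2 | 49% | 4.6 |
| 0.3 | 66% | 6.9 |
| 0.4 | 78% | 9.2 |
| 0.5 | 88% | 11.5 |

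None of these events changes the MTD decision as 5.6 is written.

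The nearest figure in the documents is in section 6: 5 of 17 patients (29%) had intractable abdominal pain at 8 g/day, given with gemcitabine. That lies inside the range. The grade is not stated, though, and any grade 3 events would already be DLTs here, so it is not used as an estimate.

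**The case against.** The strongest reply has five parts.

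- **A DLT-based MTD is a legitimate choice.** The sponsor listed the DLTs in advance and may leave grade 2 toxicity out. This stands: the point does not ask for grade 2 events to become DLTs. What is missing is a statement of how a reduced subject is counted, and sight of the reductions when the MTD is named.
- **6.4 may be meant for Part 2 only.** Its reference back to the escalation part can be read that way, and then no Part 1 subject would step down before the MTD is named. The text is not limited to Part 2, however, and on either reading grade 2 intolerance stays outside 5.6.
- **6.1 is the more specific rule for allergic events,** and a removed subject cannot take a lower dose. That is a sensible inference, but 6.4 contains no exception and a reader has to supply one.
- **Other safeguards exist.** Section 12 has the principal investigator review toxicities weekly and revise the protocol for safety, and 6.2 allows removal in the patient's best medical interest, which offers a way out at level 1. Both help individual subjects. Neither changes how the MTD is determined.
- **The over-14-day trigger can hardly arise in a 14-day course.** This is partly right, so the undefined word intolerable carries most of the weight. But sections 3 and 5.1.6 continue the rinse past day 14 when mucositis of grade 2 or less is unresolved, so the trigger is not empty.

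A reader might also infer that the four sections conflict throughout. They do not: 6.1 and 6.2 restrict only DLTs, and 6.4 mostly concerns events that are not DLTs. Nor has the trial itself judged a dose level intolerable, since 6.4 describes one subject's toxicity and not the level.

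**Conclusion.** The point holds in two limited parts. There is one direct contradiction (the intolerable or prolonged grade 2 allergic response) and one instruction that cannot be followed (6.4 at level 1). Separately, there is a gap: 5.6 ignores reductions made under 6.4, so the declared MTD can be a level that some or all of its subjects had to leave.

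The size is conditional. Over an assumed q of 0.1 to 0.5, with equal and independent risk, at least one of three subjects at a level would step down with probability 27% to 88%, and about 2 to 12 of the 23 Part 2 curcumin subjects would be reduced. Section 6 reports no major toxicity in short-term use, so the upper end should not be read as a forecast.

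A reader might be tempted to measure the gap by the chance that a level clears. Take 5.6 to mean that a level clears with 0 of 3 DLTs, or with 1 of 3 and then 0 of 3 more. At an assumed DLT risk of 10% that chance is 0.729 + 0.243 × 0.729 = 0.906. The figure is the same with no grade 2 toxicity at all, so it does not measure this problem.

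Nor do the documents show that the Part 2 comparison fails. Section 8 compares the groups by type of rinse, and nothing moves a reduced subject out of the curcumin group. The plan simply does not say how such subjects are handled or reported. Because the gap bears on the primary objective and is cheap to close, the text should be changed.

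**What to change.** 1. Reconcile 6.1, 6.2 and 6.4 so that each grade 2 event falls under exactly one rule, and cover dose level 1. Which rule governs is the sponsor's clinical decision.
2. State in 5.6 how a subject reduced under 6.4 counts at the assigned level (evaluable there or not, replaced or not). Tabulate reductions per level beside the DLT count before the MTD is named.
3. In Part 2, keep reduced subjects in their randomised arm for analysis and report how many were reduced.

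The cost is protocol wording and probably one data field: the list in section 11 does not include curcumin dose reductions, so it cannot be assumed that they are already captured. No extra subjects or visits are needed.

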6.5 Serious Adverse Events (SAEs)

SAEs are defined as:

- Death
- Life-threatening events
- Inpatient hospitalization
- Persistent or significant disability/incapacity
- Congenital anomaly or birth defects

SAEs will be reported as described in the Regulatory/Reporting Requirements section.

7. Benefits

Turmeric has been reported to be a potent anti-inflammatory and antioxidant which may be of value in treating oral mucositis. In Ayurvedic (traditional Indian) medicine, curcumin has been used for centuries as a tonic for gastrointestinal complaints. It has also been used topically in various skin diseases. Thus its safety profile in human is well documented. The antioxidant activity of turmeric can act as free radical scavengers as well as inhibitors of leukotrienes and prostaglandin synthesis. The anti-inflammatory activity has been claimed to be comparable to NSAIDs (such as indomethacin), producing significant improvement in clinical trials involving individuals with other disease such as rheumatoid arthritis. Thus our patients who suffer from cancer-treatment associate oral mucositis may benefit from curcumin as the above indicated positive effects of curcumin. Our study may offer important data for using curcumin as a new treatment for cancer patients who develop cancer treatment induced mucositis.

8. Sample Size

This study will involve 12 subjects in the first part, plus an additional 3 subjects if a dose-limiting toxicity occurs (see section 2). This sample size is similar to other phase I dose escalation studies and will result in a determination of maximum-tolerated dose. The first objective for the second part (n=46) is to determine whether curcumin decreases an objective measurement of oral mucositis. Mucositis assessment will be conducted by the provider using the WHO scale and CTCAE scale. The scales are continuous between 0 and 4. Analysis of variance will be used to compare the two groups of subjects (standard mouth rinse versus study mouth rinse) separately for each time period (baseline and each week after study mouth rinse initiation). In a one-way ANOVA study, sample sizes of 23, and 23 are obtained from the 2 groups whose means are to be compared. The total sample of 46 subjects achieves 91% power to detect differences among the means versus the alternative of equal means using an F test with a 0.05 significance level. The size of the variation in the means is represented by their standard deviation which is 0.50. The common standard deviation within a group is assumed to be 1.00.

9. Measurement of Effect

Differences between the two mouth rinse groups will be studied with the chi-square test for categorical factors and the analysis of variance F-test for continuous variables with a 0.05 significance level.

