2. Objectives/Endpoints

The primary objective of this Phase I/II study is to determine the maximum tolerated dose (MTD) of oral curcumin in patients who have chemotherapy-induced mucositis. The secondary objectives of this study are to determine whether oral curcumin:

- Decreases an objective measurement of oral mucositis
- Decreases the pain associated with oral mucositis
- Decreases the duration of mucositis
- Has an acceptable safety profile.

3. Study Design

This is a phase I/II study involving 2 parts: a dose escalation part and an expansion at the maximum tolerated dose.

In the first part, there will be 3 subjects at each dose level of curcumin (see table below). The doses will be taken 3 times each day for 14 days. Each dose will be taken as a mouth rinse containing curcumin and water, 3 times each day for 14 days. The mouth rinse will be used for 30 seconds and then swallowed. Subjects will be evaluated for dose-limiting toxicity (DLT, defined in section 6.1). The maximum tolerated dose (MTD, defined in section 2) will be determined. Subjects may participate in the study at a higher dose level, after they have completed the study at the current dose level and if they are eligible.

# Subjects	Curcumin/dose (gram)	Curcumin/day (gram)
3	0.33	1
3	1.0	3
3	2.0	6
3	3.0	9

In the second part of the study, there will be 23 subjects enrolled to an experimental (curcumin) arm and 23 subjects enrolled to a control (standard of care) arm. Subjects will be randomized to take a mouth rinse with or without the MTD of curcumin, 3 times each day for 14 days. The rinses will be swallowed. Subjects will be evaluated for response and toxicity. Subjects in the first part of the study may participate in the second part of the study, if they are eligible.

In both parts of the study, if the mucositis score \leq Grade 2 but is unresolved after 14 days of taking the study mouth rinse (curcumin or control), then the subject will

continue to receive the study mouth rinse until the mucositis is resolved (Grade 0).

This study will involve 12 subjects in the first part, plus an additional 3 subjects if a dose-limiting toxicity occurs (see section 2) and 46 subjects in the second part for a total of 61 subjects. This study is expected to take 2 years to complete enrollment, treatment and follow-up (6 months for the first part and 18 months for the second part).

4. Subject Selection

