This visit will occur 7 days (+/- 1 day) after Visit 2. A mucositis assessment (CTAE version 4.0 and WHO Oral Toxicity Scale) will be conducted and documented by a health provider (Appendix B), who will also review and follow up on any side-effects that the subject is experiencing and check the daily log (Appendix A) to ensure that the subject is complying with the study. Sufficient mouth rinse will be given to the subject for the second week of the study. A blood sample will be obtained to assess liver function (CMP) and clotting function (PT and INR). A blood and saliva sample will be obtained for research purposes (section 10). This visit will take approximately 30 minutes.

5.1.5 Phone call 2

On day 10 or 11 after the first day of taking the mouth rinse for the study, the subject will be called by a study staff member, who will review and follow up on any side-effects that the subject is experiencing and answer any questions about the study or study mouth rinse. The staff member will remind the subject to complete a subject self-assessment tool (Appendix C) and the daily log (Appendix A) and bring them to the next visit. The phone call will take about 15 minutes.

5.1.6 Visit 4

This visit will occur 7 days (+/- 1 day) after Visit 3. A mucositis assessment (CTAE version 4.0 and WHO Oral Toxicity Scale) will be conducted and documented by a health provider (Appendix B), who will review and follow up on any side-effects that the subject is experiencing and obtain the daily log (Appendix A) from the subject. A blood sample will be obtained to assess liver function (CMP) and clotting function (PT and INR). A blood and saliva sample will be obtained for research purposes (section 10). If the mucositis score \leq Grade 2 but is unresolved, then the subject will continue to receive the study mouth rinse (curcumin or standard mouth rinse) until the mucositis is resolved (Grade 0). Sufficient mouth rinse will be given to the subject for the subsequent week of the study. This visit will take approximately 30 minutes.

5.1.7 Phone call 3

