5.2 Study Calendar

Study Procedure	Visit 1 (Screening)	Week 1		Week 2		Week 3		Week 4- mucositis resolution		Final visit
	day -1	Visit 2: day 0	Phone call 1: day 3	Visit 3: day 7	Phone call 2: day 10	Visit 4: day 14	Phone call 3: day 17	Visit: For phase II: weekly cycle repeated until mucositis is resolved (and no AEs)	Phone calls	
activity window		At or w/in 48hr of Visit 1	+ 1 day	+/- 1 day	+ 1 day	+/- 1 day	+ 1 day	+/- 1 day	+ 1 day	+/- 1 day
Sign Informed Consent	X									
Oral exam for hygiene	X									
Pregnancy test	X ¹									
Provider mucositis assessment ²	X	X ³		X		X		X ^a		X
Provider supplies study mouth rinse		X		X		X ^a		X ^a		X
Provider supplies study journal, self-assessment		X		X		X ^a		X ^a		X
Provider collects journal and self-assessments				X		X		X ^a		X
Remind subject to complete self-assessment		X	X		X		X		X ^a	
Blood collection for liver function (CMP) ⁴	X			X		X		X ^a		X
Blood collection for clotting (PT and INR) ⁴	X			X		X		X ^a		X
Research blood collection ⁵		X		X		X		X ^a		
Research saliva collection ⁵		X		X		X		X ^a		
Collect AEs			X	X	X	X	X	X ^a	X ^a	X
Review of concomitant medications	X	X		X		X		X ^a		X

¹ Blood or urine pregnancy test, if not already done as part of standard of care

² Includes CTAE version 4.0 and WHO oral Toxicity scale.

³ Mucositis assessment at Visit 2, only if a different day than Visit 1 (does not need to be repeated if Visit 1 and 2 are done on the same day)

⁴ Does not need to be repeated if already done for standard of care.

⁵ 6 ml of peripheral blood into a non-anti-coagulated tube, 2 ml saliva into a sterile tube; processed and stored as described in the operations manual.

^a Only if subject is still taking study mouth rinse based on improvement of mucositis at each visit, beginning at visit 4.

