9.1 Determination of objective measurement of oral mucositis

The objective measurements of oral mucositis will be obtained by a health provider's assessment of mucositis. Providers will be uninvolved, trained oncology clinic staff (not affiliated with the study) to reduce bias. Providers will use the Common Terminology Criteria for Adverse Events (CTCAE) Version 4.0 and World Health Organization's (WHO's) Oral Toxicity Scale (OTS). They will be instructed to circle where on the scale they would assess the subject's mucositis level. A baseline evaluation will occur prior to study mouth rinse administration, and then each week after study mouth rinse initiation. The Health Care Provider Assessment Tool is attached as Appendix B.

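### The only powered comparison in Part 2 names no deciding scale or visit: arms are compared by ANOVA at every week, with two scales in play, each comparison at 0.05 with no adjustment or testing order.

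*Combined protocol and SAP*

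**What the plan says.** Section 2 makes dose finding the study's primary aim: "The primary objective of this Phase I/II study is to determine the maximum tolerated dose (MTD) of oral curcumin". The effect on an objective mucositis measure is listed there as a secondary objective. Section 8 nevertheless calls it the first objective of the second part and gives it the only power statement in the plan.

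For that objective, Section 8 says:

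- on measurement: "Mucositis assessment will be conducted by the provider using the WHO scale and CTCAE scale";
- on analysis: "Analysis of variance will be used to compare the two groups of subjects (standard mouth rinse versus study mouth rinse) separately for each time period", the periods being baseline and each week after the rinse is started;
- on power: "The total sample of 46 subjects achieves 91% power to detect differences among the means", from a one-way ANOVA F test at 0.05.

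Section 9 repeats the 0.05 level for every comparison between the rinse groups. Section 9.1 lists both scales again, ranks neither, and sets the schedule: "A baseline evaluation will occur prior to study mouth rinse administration, and then each week after study mouth rinse initiation". Section 9.6 sends group differences in response rate back to the ANOVA of Section 8 without defining response, scale or visit.

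Visit 4 is singled out only in Section 6.3. That is a lack-of-activity rule on the first 10 curcumin subjects. It involves one arm and cites both scales, so it does not define the comparison between arms.

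**The concern.** The Precis says that the response analysis will determine whether curcumin reduces mucositis. That is a yes-or-no answer, and 46 of the planned 61 subjects are enrolled to obtain it. The plan leads instead to several results, by scale and by week, each judged at 0.05. It does not say how these become one answer. If WHO and CTCAE disagree, or week 1 and week 2 disagree, the plan cannot settle the matter, and the choice would be made with the results in view.

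Two things are at stake: whether a positive statement about curcumin has the error rate a reader would take from 0.05, and whether the 91% describes the test that will be used.

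**Working it through.** **1. The plan's own power figure.** Inputs from Section 8: 23 per arm, SD of the two means 0.50, within-group SD 1.00, level 0.05.

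- With two groups, the SD of the means is half their difference, so the difference is 2 × 0.50 = 1.0 grade.
- Noncentrality = n × difference² / (2 × SD²) = 23 × 1² / (2 × 1²) = 11.5, with 1 and 44 degrees of freedom.
- Power = 91.2%. The stated 91% is reproduced, for one test.

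**2. Number of tests.** There are two scales and no combined score, so one set of tests per scale is the natural reading, although Section 8 does not literally say so. The weekly assessments have no fixed end: Visits 3, 4 and 5, then weekly until resolution. Baseline is left out below because it is not an efficacy comparison.

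- Weeks 1 and 2 (the 14-day course): 2 × 2 = 4 tests.
- Adding week 3: 2 × 3 = 6 tests.

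**3. Chance of a false claim for curcumin if any one significant result counted.** One two-sided test at 0.05 gives 0.05 / 2 = 2.5% in curcumin's favour. For several tests the answer depends on correlations that the documents do not give. The calculation draws correlated normal test statistics, takes the correlation between tests as scale correlation times week correlation, and counts the draws in which any statistic exceeds 1.96 in curcumin's favour (1,000,000 draws).

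| Assumed correlation (scales / weeks) | 4 tests | 6 tests |
|---|---|---|
| 0.6 / 0.5 | 7.8% | 10.6% |
| 0.95 / 0.8 | 5.0% | 6.2% |

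Repeating this with whole grades 0-4 (t-tests, 23 per arm, an assumed 15%, 50% and 70% at grade 0 in weeks 1, 2 and 3) gives about 6-8% for 4 tests and 8-11% for 6. The finding does not depend on normality.

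**4. Power if one test is named, or if all are kept.**

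- One named scale and visit: 91.2% with 23 per arm.
- All tests kept with Bonferroni: 4 tests, level 0.05 / 4 = 0.0125, power 78.0%; 6 tests, level 0.05 / 6 = 0.0083, power 73.2%.

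**5. Adjusting for baseline grade.** ANCOVA divides the residual SD by a factor 1/√(1 − r²), where r is the correlation between baseline and outcome, and leaves 43 degrees of freedom.

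- r = 0: 91.2%. r = 0.15: 91.8%. r = 0.29: 93.4%.
- The range 0.15-0.29 assumes that 60/35/5% of subjects enter at grades 2/3/4 (SD 0.59), with slopes of 0.25-0.5.
- Section 4.1 admits grade 2 or above, while Section 5 starts the rinse above grade 2. These passages must be reconciled. If entry were above grade 2, r would be about 0.08-0.17 and power about 91.4-92.0%.

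**6. Which visit.** Visit 4 closes the 14-day course, and Section 5.1.6 sets the provider assessment without a condition: "This visit will occur 7 days (+/- 1 day) after Visit 3. A mucositis assessment (CTAE version 4.0 and WHO Oral Toxicity Scale". Afterwards Section 6.2 removes subjects for "No improvement in mucositis after 14 days of taking the study mouth rinse", and the calendar's weekly assessments carry the note "Only if subject is still taking study mouth rinse based on improvement of mucositis at each visit, beginning at visit 4". The Visit 5 text and the calendar's final-visit column do not repeat that condition. Who is assessed after Visit 4 is therefore unclear, and later weeks may rest on selected subjects.

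**The case against.** The strongest reply is that the error rates come from a decision rule the plan does not contain. A reader might infer that the trial has a false-positive rate of up to 11%. The documents do not support that: nothing says any one significant result counts as success, and every correlation above is assumed. What is shown is an undefined deciding test; the percentages give only the consequence of one reading left open.

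Second, this is a secondary objective of a small phase I/II study, where unadjusted secondary tests are common. That limits the weight of the missing adjustment. It does not supply a deciding scale or visit for the question that sets the size of Part 2.

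Third, the 14-day course and the Visit 4 rule in Section 6.3 both point towards day 14. This makes the 2-week figures the more natural case, but neither passage defines the between-arm test.

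Fourth, Visit 4 is not free of selection. Section 6.2 also removes subjects for dose-limiting toxicity, withdrawal, physician judgement and non-compliance, and these can occur before day 14. This stands. Visit 4 avoids only the removal for lack of improvement.

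Fifth, baseline adjustment is close to a preference. A reader might infer that ANOVA without the baseline grade is wrong. It is not: in a randomised comparison the unadjusted test is valid, and the gain is at most about two percentage points of power under the assumptions shown.

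**Conclusion.** The point holds as a gap in specification. The first objective of Part 2 has no deciding test, and no other section of the supplied text fills the gap. It should be closed before Part 2 randomisation.

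The 91% is not an error, but it applies to a single comparison that the plan does not identify. If any one result were allowed to carry the claim, the chance of a false claim for curcumin would be about 5-8% with two weeks counted and 6-11% with three, against 2.5%. This rests on the assumed correlations, on two sets of tests, and on a success rule that the plan neither states nor excludes. The need to name one scale and one visit does not depend on any of those assumptions.

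**What to change.** Before Part 2 randomisation, replace the ANOVA sentence in Section 8 with:

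> 'The deciding comparison for the first objective of the second part is the provider-assessed WHO grade at Visit 4 (day 14), tested once at 0.05 by ANCOVA with arm and baseline WHO grade. CTCAE grade and the other weeks are supportive and reported with 95% confidence intervals. Baseline grades are summarised by arm without a test.'

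The sponsor may name CTCAE instead, with the baseline grade on the same scale, but the text must name one.

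Align three other places:

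- **Section 8, power:** state that the 91% is for this single comparison. The one-way ANOVA calculation can stay, since ANCOVA gives 91.2% even at zero baseline correlation.
- **Section 9:** exempt the supportive scale and weeks from the F-test at 0.05.
- **Section 9.6:** replace the sentence that sends response rate to ANOVA with a reference to this comparison. Which subjects are analysed under 9.6 is a separate question that this wording does not settle.

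The cost is wording only, with no new data, visits or subjects. The other scale and the other weeks can no longer carry a claim on their own, and ANCOVA uses one degree of freedom.
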